After 32 weeks (\pm 14 days) on the medication, only those participants who have lost $\geq 10\%$ of their baseline weight and are still on treatment with LIRA 3mg will be offered another 20 weeks on LIRA 3mg. Participants who have not met this weight loss target will have their LIRA 3mg treatment stopped but will still continue in the targeted prescribing pathway but will receive standard care only during the remainder of the study.

3rd stopping rule: After the first year of treatment (week 52; \pm 14 days), only those participants who have lost $\geq 15\%$ of their baseline weight and are still on treatment with LIRA 3mg will be offered another 52 weeks on LIRA 3mg. Participants who have not met this weight loss target will have their

LIRA 3mg treatment stopped and will still continue in the targeted prescribing pathway but will receive standard care only during the remainder of the study.

Participants who fail to reach the pre-defined weight-loss targets to continue LIRA 3mg treatment, or who choose to stop receiving LIRA 3mg, will continue to be offered the standard care provided by the Tier 3 service. These participants will still attend the Clinical Review Visits but not the additional visits for participants who are still on LIRA 3mg (e.g. Weeks 65 & 91) because these visits will not be relevant to them; visits at Weeks 65 and 91 are intended to provide a new prescription of LIRA 3mg and to discuss adherence and any side effects; see Appendices 2 & 3).

Participants will remain routinely in the Tier 3 service in-line with NICE guidance throughout the duration of the research study. Participants may be offered treatment options within the duration of the study, including bariatric surgery, as per NICE guidance and according to the decision of the local Tier 3 Multidisciplinary Team. Participants who have undergone bariatric surgery after randomisation will only be included in the intention to treat (ITT) analysis. This decision was made because the proportion of participants undergoing bariatric surgery is likely to be unbalanced between the treatment groups (i.e. more participants in the control group are expected to have bariatric surgery than in the targeted prescribing pathway treatment group), and thus weight loss in these individuals could unduly influence the study results. Participants who have been prescribed and start anti-obesity medication (such as Orlistat) will be ineligible for LIRA 3mg treatment.

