Compliance of patient with the treatment and patient related outcomes

- The number of participants who did or did not attend at least 70% of the scheduled appointments with the Tier 3 service (completers)
- The number of participants who had to stop treatment with LIRA 3mg because of adverse effects
- The adherence of participants with the LIRA 3mg (monitored through specific questionnaire and return of used pens)
- The number of participants who stopped LIRA 3mg at 16 weeks after randomisation
- The number of participants who stopped LIRA 3mg at 32 weeks after randomisation
- The number of participants who stopped LIRA 3mg at 52 weeks after randomisation
- The number of participants who completed 52 weeks of the Tier 3 service programme despite stopping LIRA 3mg at 16 weeks
- The number of participants who completed the 52 weeks of Tier 3 service programme despite stopping LIRA 3mg at 32 weeks
- The number of participants in the treatment group who had to stop treatment with LIRA 3mg because of side effects
- The number of participants started on anti-obesity drugs

Physical activity assessment

- International physical activity questionnaire (IPAQ- Long Form)

Table 1: Variables collected in this study and whether these measurements are routinely collected as part of the Tier 3 service or whether they will be additional as part of this study.

Measurement	Outcomes	Standard Care	Research
Body weight	-% Change (absolute change, relative change, proportion of participants reaching weight loss of $\geq 5\%$, $\geq 10\%$ and $\geq 15\%$ [primary outcome], proportion of participants maintaining weight loss)	X X	
Height		X	
Waist circumference		X	
Blood pressure	-Proportion of participants with hypertension (defined as patients on antihypertensive medications or systolic blood pressure $> 140\text{mmHg}$) -Dose, class of medication, and number of agents for hypertension	X X	
Heart rate		X	
Blood sample	-HbA1c -Lipid profile (including LDL & HDL cholesterol & triglycerides) -Renal profile (including U&E's, creatinine, eGFR) -Liver function test (LFTs) (including ALT, ALP, Bilirubin, Albumin) -Thyroid function test (TFTs) (including Free Thyroxine, Thyroid Stimulating hormone) -Haematology profile (including full blood count) -Amylase	X X X X X X X	X
Urine sample	-ACR -Pregnancy testing		X X

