8.8.3 Permanent treatment discontinuation (outside of the pre-specified stopping rules)

Permanent treatment discontinuation is any treatment discontinuation associated with the definitive decision from the PI or the participant not to re-expose the participant to the LIRA 3mg treatment at any time. This definition is not the same as treatment discontinuation due to a participant not meeting the weight-loss targets at the pre-specified stopping rules as per the protocol.

Participants may withdraw from treatment with the investigational drug if they decide to do so, at any time and for any reason. The PI may also decide to withdraw a participant from the study based on an inability of the subject to adhere to the obligations of the study or for the safety of the participant. Items that will lead to permanent discontinuation in the study include:

- Pregnancy
- Episode of acute pancreatitis (only for participants in LIRA 3mg group)
- Breast malignancy (only for participants in LIRA 3mg group)
- They repeatedly violate or are non-compliant with the protocol
- Where LIRA 3mg doses are not tolerated by the participant
- Any other contraindication to the study medication which the PI determines to require permanent treatment discontinuation.

*Please note if a participant's amylase result is within the normal range but the study clinician suspects acute pancreatitis a lipase test will be conducted.

All efforts should be made to document the reasons for treatment discontinuation and this should be documented in the CRF and medical records.

Any abnormal laboratory value that in the opinion of the clinician may be an indication for discontinuing the treatment of a participant will be rechecked by the PI or second clinician if the first clinician is the PI for confirmation before making a decision of permanent discontinuation of the investigational drug for the concerned participant. Threshold values for the discontinuation of investigational drug use shall be defined in collaboration with the Sponsor representative. The values will be adapted to the population studied, as appropriate.

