Stopped LIRA 3mg	16, 32, 52	Binary indicator of 1 if participant stopped treatment with LIRA 3mg at time-point (i.e., due to stopping rules or side effects), 0 otherwise. Only defined for participants in intervention arm who were on LIRA 3mg treatment at the previous time-point.
Completed 52 weeks of the Tier 3 service programme despite stopping LIRA 3mg at 16 weeks	52	Binary indicator of 1 if participant completed 52 weeks of the Tier 3 service programme despite stopping LIRA 3mg at 16 weeks, 0 otherwise. Only defined for participants in intervention arm who stopped LIRA 3mg treatment at 16 weeks.
Completed 52 weeks of Tier 3 service programme despite stopping LIRA 3mg at 32 weeks	52	Binary indicator of 1 if participant completed 52 weeks of the Tier 3 service programme despite stopping LIRA 3mg at 32 weeks, 0 otherwise. Only defined for participants in intervention arm who stopped LIRA 3mg treatment at 32 weeks.
Started on anti-obesity drugs	52, 104	Binary indicator of 1 if participant started on anti-obesity drugs other than LIRA 3mg, 0 otherwise. Defined as a concomitant medication listing of Orlistat.
Physical activity assessment		
International physical activity questionnaire (IPAQ- Long Form; MET-minutes/week)	52, 104	Total MET-minutes/week calculated in line with Appendix 6 and then change from baseline calculated.

^a Glucose lowering medications are defined as metformin, a sulphonylurea, a thiazolidinedione, or a SGLT-2.

^b These are also considered safety outcomes.

^c On the CRF, hypertension is a yes/no tick box with the following wording: "Hypertension treated (antihypertensives with or without diagnosis) or untreated (systolic blood pressure >140 mmHG at two consecutive visits to Tier 3 clinic)." If a definition of anti-hypertensive medications is required for the derivation of any variables then the following medication should be considered as anti-hypertensive: ACE-inhibitors, calcium channel blockers, thiazide diuretics, alpha-blockers (e.g., doxazosin) and beta-blockers.

N.B. CPAP compliance (hours/days) was listed as a secondary outcome in the protocol but will not be reported as it hasn't been captured in the database.

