Total Leisure-Time MET-minutes/week = sum of Walking + Moderate + Vigorous MET-minutes/week scores in leisure.

Total Scores for all Walking, Moderate and Vigorous Physical Activities

Total Walking MET-minutes/week = Walking MET-minutes/week (at Work + for Transport + in Leisure)

Total Moderate MET-minutes/week total = Moderate MET-minutes/week (at Work + Yard chores + inside chores + in Leisure time) + Cycling Met-minutes/week for Transport + Vigorous Yard chores MET-minutes/week

Total Vigorous MET-minutes/week = Vigorous MET-minutes/week (at Work + in Leisure)

Note: Cycling MET value and Vigorous garden/yard work MET value fall within the coding range of moderate-intensity activities.

Total Physical Activity Scores

An overall total physical activity MET-minutes/week score can be computed as: Total physical activity MET-minutes/week = sum of Total (Walking + Moderate + Vigorous) METminutes/week scores.

This is equivalent to computing: Total physical activity MET-minutes/week = sum of Total Work + Total Transport + Total Domestic and Garden + Total Leisure-Time MET-minutes/week scores.

As there are no established thresholds for presenting MET-minutes, the IPAQ Research Committee proposes that these data are reported as comparisons of median values and interquartile ranges for different populations.

14 Appendix 7 Definitions for adherence of participants with the LIRA 3mg

Individuals that didn't receive 70% of the doses as determined by the protocol (i.e. in the first 16 weeks or there after whilst continuing to meet the continue rules of the protocolised treatment schedule) will be classed as not adhering with the LIRA 3mg pathway.

Defining days taking LIRA

The number of days taking LIRA will be calculated as the time from first dose dispensed (normally at baseline visit) to the last known date of individuals taking the LIRA. Where individuals are recorded as not completing the trial due to stopping the LIRA, the date of last dose of LIRA in the completion form will be used; if this is not recorded then the date of first visit at which individuals say they are not happy to continue taking LIRA will be used; and where neither of these are recorded the date of the last visit that individuals said they are happy to continue LIRA will be used.

14.1 52 weeks

Individuals will then be assessed for whether they have received 70% as per table below.

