16.14 Summary of categorical compliance outcomes

Outcome	N (%) at baseline		N (%) at follow-up	
	Control	Intervention	Control	Intervention
Attended at least 70% of scheduled Tier 3 appointments at 52 weeks				
No				
Yes				
Missing				
Attended at least 70% of scheduled Tier 3 appointments at 104 weeks				
No				
Yes				
Missing				
Stopped treatment with LIRA 3mg due to adverse effects at 52 weeks				
No				
Yes				
Missing				
Stopped treatment with LIRA 3mg due to adverse effects at 104 weeks				
No				
Yes				
Missing				
Compliant with LIRA 3mg treatment at 52 weeks				
No				
Yes				
Missing				
Compliant with LIRA 3mg treatment at 104 weeks				
No				
Yes				
Missing				
Stopped LIRA 3mg treatment at 16 weeks				
No				
Yes				
Missing				
Stopped LIRA 3mg treatment at 32 weeks				
No				
Yes				
Missing				
Stopped LIRA 3mg treatment at 52 weeks				
No				
Yes				

Outcome	N (%) at baseline		N (%) at follow-up	
	Control	Intervention	Control	Intervention
Missing				
Completed 52 weeks of the Tier 3 programme despite stopping LIRA 3mg at 16 weeks				
No				
Yes				
Missing				
Completed 52 weeks of the Tier 3 programme despite stopping LIRA 3mg at 32 weeks				
No				
Yes				
Missing				
Started on anti-obesity drugs at 52 weeks				
No				
Yes				
Missing				
Started on anti-obesity drugs at 104 weeks				
No				
Yes				
Missing				

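### The SAP's 'Stopped LIRA 3mg' indicator counts only stops due to stopping rules or side effects, so some participants who stop by choice would be tabulated as not stopped.

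*SAP*

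**What the plan says.** SAP 2.2.1, under compliance, defines 'Stopped LIRA 3mg' at weeks 16, 32 and 52 as: "Binary indicator of 1 if participant stopped treatment with LIRA 3mg at time-point (i.e., due to stopping rules or side effects), 0 otherwise". It restricts the denominator: "Only defined for participants in intervention arm who were on LIRA 3mg treatment at the previous time-point". The results go into SAP Table 16.14, in rows such as "Stopped LIRA 3mg treatment at 16 weeks", with the categories No, Yes and Missing.

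The outcome comes from the compliance list in Protocol 6.4.2: "The number of participants who stopped LIRA 3mg at 16 weeks after randomisation", with matching items for 32 and 52 weeks. None of the three names a reason. Stops because of adverse or side effects are separate items in that list, and SAP 2.2.1 also gives adverse-effect stops their own indicator.

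Stopping by choice is expected. Protocol 6.2, in text repeated in SAP 1.2.3.1, places people who miss the weight targets beside those "or who choose to stop receiving LIRA 3mg". Protocol 8.8.3 is broader: "Participants may withdraw from treatment with the investigational drug if they decide to do so, at any time and for any reason". It also lists pregnancy and repeated non-compliance among the grounds for permanent discontinuation.

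SAP 5.8, which records departures from the protocol, does not mention this outcome.

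**The concern.** The abbreviation 'i.e.' makes the two named reasons exhaustive, and the closing words send every other case to 0. A stop by personal choice, or for another unlisted reason such as pregnancy, is neither a stopping-rule stop nor a side-effect stop. An analyst who programs the definition as written would report such a person as not having stopped.

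The number who stopped LIRA at each decision point is a listed secondary outcome. It helps show how the prescribing pathway works in practice, because voluntary stopping is one of the ways people leave the drug. SAP 2.2.1 contains no other all-cause stopping outcome. The CONSORT diagram in SAP 5.1 will show reasons for stopping, so two outputs of one report could give different totals.

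**Working it through.** The plan states no figure for this outcome, so there is nothing to reproduce. The check is a reading of the definition, followed by an illustration of size.

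**Step 1: apply the definition to a case.** Take an intervention participant who starts LIRA at baseline, quits by choice at week 10, attends week 16 and has lost at least 5% of baseline weight.
- Denominator: on LIRA at the previous time-point (baseline), so included at week 16.
- Stopping rule: the 5% target is met, so the rule did not stop treatment.
- Side effects: not the reason.
- Result: coded 0 and counted under 'No' in Table 16.14, although off the drug.

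**Step 2: a case that is not clearly wrong.** If the same participant has lost less than 5%, the week-16 rule would also have ended treatment, and the code may be 1. The SAP gives no order of precedence between reasons. The clear miscoding is therefore among quitters who attend and meet the target.

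**Step 3: size at week 16.**

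Inputs:
- 261 intervention participants (Protocol 11.2).
- Share stopping by choice or another unlisted reason before week 16: not in the documents; assumed 5-15%.
- Share missing the 5% target at week 16: not stated directly. Protocol section 4 gives 24.2% of early responders and 1.8% of early non-responders reaching 15% weight loss, and 14% overall. If r is the responder share, 24.2r + 1.8(1 - r) = 14, so r = (14 - 1.8)/(24.2 - 1.8) = 12.2/22.4 = 54.5%. The share missing the target is then 45.5%, or about 46%.

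Calculation:
- Quitters: 0.05 x 261 = 13; 0.15 x 261 = 39.
- Quitters who meet the target, if quitting is independent of weight loss: 13.05 x 0.545 = 7; 39.15 x 0.545 = 21.
- Shortfall in the reported share: 0.05 x 54.5% = 2.7 points; 0.15 x 54.5% = 8.2 points.

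Leaving side-effect stops aside, the literal 'Yes' count is 0.455 x 261 = 119, against 119 + 7 = 126 to 119 + 21 = 140 for all-cause stopping.

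**Step 4: bounds.** If quitters lose less weight than others, more of them miss the target and fewer than 7-21 are miscoded. If none miss it, all 13-39 are (5-15 points).

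**The case against.** The main clause of the definition is general, and the reasons stand in brackets, so 'i.e.' may be a slip for 'e.g.'. Weeks 16, 32 and 52 are also the three stopping-rule decision points, so the protocol items could mean stops made at those visits rather than all stops. An undeclared narrowing is then arguable rather than certain. This stands in part. But the SAP adds side effects to the row, so it does not follow a rule-only reading either, and the protocol names a reason elsewhere in the same list when it intends a limit. The wording needs settling on either view.

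Some information is also available elsewhere. SAP 5.1 puts reasons for stopping in the CONSORT diagram, with counts for each stopping rule, and SAP 5.7 adds a treatment-flow figure. Appendix 7 measures adherence to the last known date of use, whatever the reason. This stands and limits the consequence, but it does not correct the table row.

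A reader might infer more than the text supports:
- **That the error carries forward to weeks 32 and 52.** The denominator is actual drug status at the previous time-point, not the previous value of the indicator. Someone off the drug at week 16 is outside the week-32 denominator.
- **That quitters are excluded from the two outcomes on completing Tier 3 despite stopping LIRA.** Those rows refer to participants who stopped, without citing this indicator or limiting the reason.
- **That participants lost to contact are coded as not stopped.** They may fall under 'Missing'. By analogy with Appendix 7, which groups an unmeasured weight with a missed target, they may instead count as stopped by the rule.
- **That Table 16.14 reports quitters as still taking LIRA.** It records 'No' to having stopped, which is not quite the same statement.
- **That the share stopped is 5-15 points too low.** That holds only if no quitter would also miss the weight target.

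**Conclusion.** The point holds as a defect of definition. As worded, the indicator leaves out stops that both documents foresee, and no other section overrides it. Quitters who attend and meet the weight target would be counted as not stopped.

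The illustrative size at week 16 is 7-21 of 261 people, or 3-8 percentage points. This rests on three assumptions: a voluntary-stop rate of 5-15%, a 46% share missing the target, and independence of the two. The 46% combines an overall trial result with separately cited post-hoc rates whose denominators the documents do not show, so it is only a rough guide.

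The consequence is modest. SAP 5.5.1 treats compliance outcomes descriptively, and the primary analysis, per-protocol set and adherence rule do not use this indicator. It should still be corrected, because it is a listed secondary outcome and the correction costs almost nothing.

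**What to change.** In SAP 2.2.1, set the indicator to 1 for any cessation of LIRA since the previous time-point, whatever the reason, dated by the last-use rule in Appendix 7. That rule already covers refusal to continue: where no last-dose date is recorded, "the date of first visit at which individuals say they are not happy to continue taking LIRA will be used". In addition:
- tabulate the reason in Table 16.14 (stopping rule, adverse effect, participant choice, other), with a stated order of precedence when two apply;
- code unknown drug status as missing, not 0;
- use the same all-cause definition for the two rows on completing Tier 3 despite stopping LIRA;
- reconcile the totals with the CONSORT diagram.

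If a rule-or-side-effect count is really intended, the row should be labelled so and the change listed in SAP 5.8.

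The cost is a line or two of wording and a few table rows. Protocol 8.8.4 already requires discontinuations outside the stopping rules to be documented in the CRF, and the SAP's adverse-effect indicator draws on a recorded main reason. The SAP is marked as a draft and provides for amendment before database lock.

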2.3 Subgroups and/or interactions

No subgroup or interaction analyses are planned.

2.4 Compliance

For assessing the impact of compliance on the effectiveness of the intervention, , compliance is defined as:

Participants in the standard care group are defined as treatment compliant if they complete at least 70% of the planned contacts in the Tier 3 service. Participants in the intervention group are defined as treatment compliant if they complete at least 70% of the planned contacts in the Tier 3 service, and take at least 70% of their planned doses of LIRA 3mg as stipulated by the prescribing pathway.

Compliance variables are listed in Section 2.2.

A binary variable of compliant with tier 3 service captures whether a participant has been compliant with the planned contacts in Tier 3 service (see section 3.3.3).

2.5 Other

There are no other variables to be presented in the statistical report which are not outcomes, baseline or demographic variables, or for measuring compliance or safety.

3 Analysis Sets/Populations

3.1 Disposition of participants

Screened patients

Screened patients are defined as any patient who met the inclusion criteria and signed the informed consent form.

Treated patients

Treated patients consist of all patients, who have been allocated to one of the two treatment groups, and have at least partially completed the Baseline Visit.

Data from all randomised participants will be used in the study final report and analysis, with data analysed in the group to which the participant was randomised.

3.2 Protocol deviations

The following deviations were captured in the protocol deviation Case Report Form:

Participant ineligible for entry into trial
Participant deviated from randomised treatment group
Participant's visit/assessment not performed as per protocol
Non-permitted treatment
Trial Specific Issues
Other deviation

No protocol deviations will result in systematic exclusion from all statistical analyses. Reasons for exclusion/inclusion in each population are described in 3.3. below.

3.3 Populations

All treated patients will be included in the Intention-To-Treat (ITT) population as a minimum. Patients who were screened, but not treated, will not be included in any of the analysis populations.

3.3.1 Complete Cases Population

The complete cases population is defined as all randomised participants who have data available for the outcome being analysed, according to the study group to which they were randomised at baseline. Participants who had bariatric surgery during the study period will be only be included at time-points prior to their bariatric surgery. They will be excluded from time-points after their bariatric surgery.

